3.5 Secondary Study Endpoints

NONE

3.6 Primary Safety Endpoints

Since C-11 choline is an essential nutrient needed for physiologic process as an integrated part of cell membrane component, and the quantities actually administered are in the micromolar range, there are no expected adverse reactions due to the primary study drug. The primary safety endpoint would be documentation of either lack of reaction to C-11 choline injection or detailed description of any adverse reaction (rash, fever, hypotension, dyspnea, chest pain) and treatment measures undertaken.

3.7 Identification of Source Data

The following source data will be directly recorded on the Case Report Form (CRF):

- Vital signs
- Events
- Dosage of C-11 choline, route of administration
- Patient Reported Outcomes

The following source data will not be directly collected in the Case Report Form (CRF), but will be captured in supportive documentation (study source documents, EMR):

- Laboratory results can be utilized from outside facilities for this study
- Prostate biopsy reports and pathology reports can be utilized from outside facilities for this study.

4 Subject Selection Enrollment and Withdrawal

4.1 Inclusion Criteria

- Adults, age 18 and older
- Untreated male patients with high-risk and very high-risk prostate cancer, who require clinical pelvic mpMRI, CT, and bone scan as standard clinical care for diagnosis and management of prostate cancer.

4.2 Exclusion Criteria

- Patients who already received primary treatment or neo-adjuvant therapy.
- Patients who refuse undergoing routine clinical imaging (i.e., pelvic mpMRI, CT, bone scan) for staging. Reimbursement of pelvic mpMRI may be provided. CT and bone scan may be done elsewhere outside of Mayo Clinic but should be of diagnostic quality. Research C-11 choline PET/MR will not substitute pelvic mpMRI, CT, or bone scan in this study.
- Patients cannot tolerate MRI (e.g., claustrophobia, severe back pain or spasm, involuntary movement [e.g., tremor, dystonia]).
- Patients have total hip arthroplasty (THA), which can cause substantial susceptibility artifact and degrade image quality of mpMRI.
- Patients have cardiac pacemaker, cochlear implants, neurostimulator, medical device which is unsafe at 3 Tesla, or foreign metallic body in the eyes or orbit.
- Patients have contraindication to gadolinium based MR contrast agents (e.g., renal failure, severe reaction to gadolinium based MR contrast agents). eGFR should be above 30 within 30 days the time of mpMRI.

4.3 Subject Recruitment, Enrollment and Screening

Subjects who are scheduled to undergo standard care of primary prostate cancer diagnosis and staging will be identified, informed about this study and referred to our study coordinator by urologists from their clinical practice schedule. C11-choline PET/MR imaging could be performed before and/or after routine clinical imaging.

4.4 Early Withdrawal of Subject

If a subject cannot finish the PET/MR imaging due to claustrophobia, he will be withdrawn. After PET/MR imaging, if a subject declines to undergo clinical evaluation and standard care of imaging, he will be withdrawn.

We plan to recruit a replacement subject in the event that a subject withdraws early to maintain the target number of 10 subjects.

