* Axial T1-weighted LAVA-FLEX acquired in Part1. may be used for pre-contrast T1-weighted images.

Image review:

- PET/MR fusion study, including PET emission data, MRAC image and focused pelvis PET/MR fusion images will be sent to MIM Vista workstation for review by an independent, experienced board certified nuclear medicine radiologist without knowing clinical findings except for high risk prostate cancer.
- Focused mpMRI of pelvis images will be sent to PACS for review by an independent, experienced board certified body MR radiologist without knowing clinical findings except for high risk prostate cancer.

Evaluation of imaging findings:

Reviewers review images to evaluation imaging findings without knowing clinical findings except all subjects are recently diagnosed with very high-risk or high-risk prostate cancer. Readout workflow is illustrated in Figure 2. The scores will be recorded and stored in a secured REDCap file.

Pelvic mpMRI:

1. Lesion detection and characterization utilizing PI-RADS version 2 (15).
2. Tumor staging utilizing AJCC TNM staging system (3)
3. Detection of suspicious pelvic lymph nodes.
4. Detection of suspicious osseous lesion in the pelvis.

Torso and focused C-11 choline PET/MR:

1. Lesion detection and characterization.
2. Tumor staging
3. Detection of suspicious pelvic and extrapelvic lymph nodes.
4. Detection of suspicious osseous lesion in the pelvis and extrapelvic regions.
5. Document SUV in the region of interest (ROI) if possible.

Reference standards

[figure not shown]
[figure not shown]

1. Histopathology results when available
2. Clinical imaging study (CT, bone scan, etc).
3. Clinical follow-up (progression or regression at follow-up routine clinical imaging after treatment).

Prostate tumor localization and characterization: Focused C-11 choline PET/MR and pelvic mpMRI findings to be correlated with clinical prostate biopsy and surgery results.

Lymph node metastases: Torso and focused C-11 choline PET/MR and pelvic mpMRI findings to be correlated with clinical CT, lymph node biopsy, and surgery results

Bone metastases: Torso and focused C-11 choline PET/MR and pelvic mpMRI findings to be correlated with whole body bone scan, F-18 NaF PET/CT (if available), CT, dedicated MRI, and biopsy results.

Figure 1. Illustration of Part 1 “Torso C-11 Choline PET/MR” and Part 2 “Hybrid Focused C-11 Choline PET/MR and Pelvic mpMRI.”

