3.4 Primary Study Endpoints

Patient: Completion of all imaging examinations with laboratory results.

Data analysis:

Objective 1: Descriptive study. With biopsy and/or surgical histopathology as gold standard, the sensitivity, specificity and accuracy of PET/MR will be calculated.

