4.4.2 Data Collection and Follow-up for Withdrawn Subjects

The C-11 choline PET/MR data will be retained for potential future analysis. Data collected on study subjects up to the time of withdrawal will remain as part of the study in a secured database in order for the study to maintain scientific validity.

Regardless of enrollment status, subjects will be contacted to collect Day 2 follow up information. This information will be recorded in the case report form documentation.

5 Study Drug

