5.9.4 Return or Destruction of Study Drug

After injection of the C 11 choline the syringe will be assayed for residual radioactivity, to be used in calculation of the precise injected dose. The syringe will then disposed of in the radioactive container for 3-4 hours, about ten half-life durations of C11-Choline (C11-Choline half-life of 20 minutes).

6 Study Procedures

Patients who have completed or will complete diagnostic body CT scan and nuclear medicine bone scan as part of standard care will be recruited and consented for participation in the study

PET/MRI is preferably scheduled 6 weeks after prostate biopsy to minimize the effects of post biopsy hemorrhage.

6.1 Day 0

Informed consent discussion with subject by research coordinator. Consent form signed by subject. Medical records will be reviewed by study coordinator. Subject's eGFR will be determined. If current serum creatinine level is unavailable, labs will be obtained for review.

Subject will be reminded to drink 48 ounces of water the day prior to study procedures. On the morning of the procedure, subjects will be counseled to fast for four hours prior to the procedure and drink 24 ounces of water.

6.2 Day 1

The patient will be screened for MR safety prior to entering the scan room, which may include the use of ferromagnetic screening.

[figure not shown]
1. Vital signs (sitting blood pressure, heart rate, respiratory rate, temperature) are measured by the radiology nurse, who records the results on the source document.
2. Investigator MD or research coordinator to see patient, review vital signs and discuss study objectives, explain the imaging procedures, answer questions. MD will sign and date the source document.
3. Subject is brought to the PET/MR imaging suite. Total dose of 12-14 mCi C-11 choline is injected I.V.
4. Torso PET/MR fusion scan is completed. Imaging time 20-30 minutes.
5. Pelvic mpMRI with PET data of pelvis completed. Imaging time 40-45.
6. Following completion of imaging, subject will return to the relax room and vital signs (sitting blood pressure, heart rate, respiratory rate and temperature) will be re-checked by

the radiology nurse, with the study coordinator recording the data in the source documents.

7. Subject will be discharged.

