7.2 Statistical Methods

Descriptive Statistics

Descriptive statistics will be used to describe the average time of the total procedure, patients' tolerance and satisfaction level about the procedure. Paired t-test will be used to compare the suspicious lymph nodes and suspicious osseous lesions in the pelvis and extrapelvic regions detected by hybrid C11-choline PET/MR and pelvic multiparametric MRI method and by conventional CT and bone scan to investigate if the new method is able to detect more lymph nodes and osseous lesions compared to the conventional method. Paired t-test will also be used to compare the average SUV of lymph nodes and osseous lesions in the pelvis and extrapelvic regions by new method with that by conventional method to investigate if the new method provided more clarity in terms detecting the lymph nodes and lesions compared to the old method. If the patients' biopsy and surgery results available, sensitivity, specificity, positive predictive value and negative predictive value of detecting malignant lymph nodes and osseous lesions by the new method and by conventional method will be estimated and compared using McNemar's test.

Handling of Missing Data

As the sample size is 20 and imaging is completed over one day, no missing imaging data is anticipated.

Multiplicity

In current project, there is one primary objective and we don't have to adjust for multiple comparison.

Interim Analysis

There will not be interim analysis for the study.

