7.3 Subject Population(s) for Analysis

All-completed population: Only subjects who completed ALL study related procedures and follow-up will be included

8 Safety and Adverse Events

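### A subject who declines standard imaging after PET/MR leaves the PET/MR-versus-histopathology analysis, which needs neither CT nor bone scan; this exclusion follows the index test and could depend on its result

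*Combined protocol and SAP*

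**What the plan says.** - **Order of scans.** Section 4.3: "C11-choline PET/MR imaging could be performed before and/or after routine clinical imaging". Section 6 (Study Procedures) recruits "Patients who have completed or will complete diagnostic body CT scan and nuclear medicine bone scan", so these scans may still be outstanding on the day of PET/MR.
- **Withdrawal.** Section 4.4: "After PET/MR imaging, if a subject declines to undergo clinical evaluation and standard care of imaging, he will be withdrawn". The same section provides for a replacement.
- **Data of withdrawn subjects.** Section 4.4.2: "The C-11 choline PET/MR data will be retained for potential future analysis". It adds that whatever was collected before withdrawal stays in the study database.
- **Analysis set.** Section 7.3 defines a single population: "Only subjects who completed ALL study related procedures and follow-up will be included".
- **Accuracy analysis.** Section 3.4: "With biopsy and/or surgical histopathology as gold standard, the sensitivity, specificity and accuracy of PET/MR will be calculated". Table 1 gives pathology as the reference standard in every row.
- **Other uses of CT and bone scan.** The list of reference standards in 3.3 also includes "Clinical imaging study (CT, bone scan, etc", and section 7 compares the new method with CT and bone scan.
- **Missing data.** Section 7.2: "As the sample size is 20 and imaging is completed over one day, no missing imaging data is anticipated".

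**The concern.** Sensitivity and specificity are fractions of diseased and non-diseased subjects classified by the index test. An exclusion decided before the index test, or unrelated to its result, leaves them unbiased. An exclusion decided afterwards may not. Here the decision to decline comes after PET/MR, and only in men scanned PET/MR-first; a man whose CT and bone scan were already done cannot be lost in this way.

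If men with a positive PET/MR declined more often, sensitivity would be understated and specificity overstated. If men with a negative PET/MR declined more often, the reverse would hold. Because each withdrawn man is replaced, the final number analysed would look complete in either case.

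For the 3.4 analysis the exclusion is also unnecessary. The man has had his PET/MR. Section 6 prefers the session to take place 6 weeks after prostate biopsy, so biopsy pathology will often exist already, and 3.7 lists biopsy and pathology reports as source documents.

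**Working it through.** **1. The plan's own figures.** The plan gives no rate of declining and no allowance for it, so there is no figure on this point to reproduce. Its one calculated figure is the 82% power in 7.1 (20 patients, two-sided 0.05, difference 0.30, discordant proportion 0.31). Miettinen's formula gives Φ[(0.30·√(20·0.31) − 1.96·0.31)/√(0.31² − 0.30²·3.31/4)] = Φ(0.139/0.147) = 82.8%, which agrees. Other McNemar power methods give other values (exact two-sided: 56.9%). That is a separate matter and does not enter here.

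**2. Who is lost.** Take a man scanned PET/MR-first who then declines standard imaging.

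| Analysis | Data it needs | Does he have them? | Is he analysed under 4.4 and 7.3? |
|---|---|---|---|
| 3.4 accuracy of PET/MR | PET/MR, histopathology | Yes, where pathology exists | No |
| Section 7 comparison with CT and bone scan | PET/MR, CT, bone scan, and pathology for sensitivity and specificity | No | No |

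The second exclusion cannot be avoided. The first follows only from the wording. The missing-data text does not cover it, because it concerns imaging done on the one study day.

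**3. What selection could do (assumptions, not plan figures).** Let Se and Sp be the true values, and let w+ and w− be the probabilities of withdrawal after a positive or a negative PET/MR. Among those retained:

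- sensitivity = Se(1−w+) / [Se(1−w+) + (1−Se)(1−w−)]
- specificity = Sp(1−w−) / [Sp(1−w−) + (1−Sp)(1−w+)]

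With Se = 0.70 and Sp = 0.80:

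| w+ | w− | Sensitivity | Specificity |
|---|---|---|---|
| 0 | 0.10 | 0.722 | 0.783 |
| 0 | 0.20 | 0.745 | 0.762 |
| 0 | 0.30 | 0.769 | 0.737 |
| 0.10 | 0 | 0.677 | 0.816 |
| 0.20 | 0 | 0.651 | 0.833 |
| 0.30 | 0 | 0.620 | 0.851 |
| 0.20 | 0.20 | 0.700 | 0.800 |

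Example, third row: 0.70/(0.70 + 0.30·0.70) = 0.70/0.91 = 0.769.

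**4. Dependence on scan order.** If a fraction f is scanned PET/MR-first and d+ and d− are the decline rates in that group, then w+ = f·d+ and w− = f·d−. With Se = 0.80, Sp = 0.90, d+ = 0.30 and d− = 0.05:

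- f = 0.5: sensitivity 0.80·0.85/(0.80·0.85 + 0.20·0.975) = 0.777; specificity 0.912
- f = 1: sensitivity 0.747; specificity 0.924
- f = 0: no shift

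Raising d+ to 0.50 gives sensitivity 0.755 (f = 0.5) and 0.678 (f = 1). The plan does not fix f.

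**The case against.** **Disclosure is not stated.** A reader might infer that men will see a clear PET/MR result and skip the remaining scans. The documents do not support that. Section 3.3 sends the PET/MR images to a workstation for an independent blinded reader and the scores to a secured REDCap file. The routing to PACS and the standard-of-care label in 6.4 concern the pelvic mpMRI, not the PET/MR reading. No passage withholds PET/MR results, but none releases them either. This part of the objection stands.

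**Refusal is made less likely.** Section 4.2 excludes men who refuse routine imaging and says the research scan is no substitute for it; 4.1 and 4.3 recruit men who need that imaging as standard care. This lowers the chance of declining but does not remove it, and 4.4 provides for the case.

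**Data are not discarded.** It would be wrong to read 4.4.2 as keeping only images. It keeps everything collected up to withdrawal, but does not cover pathology that arrives later and assigns the data to no planned analysis.

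**Section 7.3 could be read narrowly.** CT and bone scan are not in the 6.4 schedule, so they might not count as study-related. Yet a man who has been withdrawn and replaced is hard to count as a completer. The text should settle this.

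**CT and bone scan do matter elsewhere.** A claim that no PET/MR analysis needs them would go too far: the 3.3 reference list and the section 7 comparison use them. The point is confined to 3.4 and Table 1.

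**Pathology may be incomplete.** The trigger in 4.4 includes declining clinical evaluation, so nodal or bone pathology may never be obtained. All subjects have prostate cancer, so prostate biopsy alone cannot give patient-level specificity, and 3.4 does not name the target. The single-target model above is therefore only schematic.

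**Precision is low in any case.** Even 16 of 20 has an exact 95% interval of about 0.56 to 0.94, and the primary objective is feasibility.

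**Conclusion.** The point holds as a possibility created by the wording. PET/MR may come first, a man who then declines standard imaging is withdrawn and replaced, and the only analysis set removes him from an accuracy analysis for which he may have all the data. That exclusion follows the index test and is avoidable.

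The documents do not establish that declining would depend on the PET/MR result, and they give no decline rate and no share scanned PET/MR-first. Neither the size nor the direction of any bias can be determined. Under the assumed Se 0.70 and Sp 0.80, with 10 to 30% loss in one result group only, sensitivity would shift by -8.0 points (0.620 − 0.700) to +6.9 points (0.769 − 0.700), and specificity by -6.3 points (0.737 − 0.800) to +5.1 points (0.851 − 0.800). With equal loss in both groups the shift is zero. A shift of this size would lie within sampling error at 20 subjects, but the final count would not reveal it.

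A reader might also conclude that PET/MR should be required to follow CT and bone scan. That does not follow. Some men could start treatment on the earlier scans and become ineligible under 4.2, which is another possible selection on results.

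**What to change.** Reconcile 4.4, 4.4.2 and 7.3. Changing 4.4 alone is not enough, because 7.3 could still exclude the same man.

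- **4.4:** state that a subject who completes PET/MR and then declines standard imaging remains on study, unless he withdraws consent or authorization for use of his health information, and is not evaluable only for the paired comparison with CT and bone scan.
- **4.4.2:** state that, subject to the same proviso, his pathology is collected from the medical record and his data enter the 3.4 analysis.
- **7.3:** define two populations. For 3.4: all subjects with a completed PET/MR and available histopathology. For the paired comparison: those who also have CT and bone scan.
- **Reporting:** give the scan order and PET/MR result of every subject who declines, so that readers can judge any selection left in the paired comparison.

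The order of scans need not change. While 4.4 is open, its replacement target of 10 should be reconciled with the 20 in 3.2 and 7.1.

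Cost: protocol wording and one CRF field for scan order. The two analyses may have different numbers of subjects, and nodal or bone pathology may be missing for some men who are kept.

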4.4.1 When and How to Withdraw Subjects

Subjects may be withdrawn from the study if consent is withdrawn, if they no longer satisfy enrollment criteria or if they are unable to continue participation due to discomfort.

4.4.2 Data Collection and Follow-up for Withdrawn Subjects

The C-11 choline PET/MR data will be retained for potential future analysis. Data collected on study subjects up to the time of withdrawal will remain as part of the study in a secured database in order for the study to maintain scientific validity.

Regardless of enrollment status, subjects will be contacted to collect Day 2 follow up information. This information will be recorded in the case report form documentation.

5 Study Drug

5.1 Description

C-11 choline is identical to endogenous choline in the human body. Choline is a central molecule in cellular metabolism via the citric acid cycle (as acetyl CoA), in cell membrane fatty acid synthesis, and in gene expression regulation through acetylation of nuclear histones.

5.2 Treatment Regimen

A total of 12-14 mCi,(444-518 MBq) doses are dispensed. The doses are described based on the amount of radioactivity since the actual quantity of choline is in the micromolar range, as is true for many radiopharmaceuticals.

5.3 Method for Assigning Subjects to Treatment Groups

All study subjects will undergo the same protocol.

5.4 Preparation and Administration of Study Drug

Choline C11 Injection is prepared on site at the Mayo Clinic PET Radiochemistry Facility in Phoenix, AZ. Cyclotron produced C11-carbon dioxide is used as a precursor to generate C11-methyl iodide followed by C11-choline. All chemistry is performed using automated radiochemical synthesizers inside lead-lined hot cells.

Following quality control testing, the drug product is packaged in a 6 mL sterile shielded syringe containing approximately 12-14 mCi. .

5.5 Subject Compliance Monitoring

C-11 choline is only administered under direct supervision of study personnel.

5.6 Prior and Concomitant Therapy

None.

5.7 Packaging

The drug product is packaged in a 6 mL sterile syringe containing approximately 12-14 mCi of radioactivity. It is placed inside a lead syringe shield and labeled with the date, batch number, radioactive assay, drug product name, and the following statement “Caution: New Drug— Limited by Federal (or United States) law to investigational use”. It is then placed inside specially designed tungsten lined pneumatic tube capsule and sent to the PET imaging suite.

5.8 Masking/Blinding of Study

The interpreters of the imaging tests will be blinded to any patient information. However, the type of tracer and imaging approach will be apparent due to inherent differences in the techniques.

5.9 Receiving, Storage, Dispensing and Return

5.9.1 Receipt of Drug Supplies

The drug product will be manufactured on the same campus as the imaging suite and will be delivered via pneumatic tube.

5.9.2 Storage

Choline C 11 Injection should be stored at 25°C (77°F); excursions permitted to 15 to 30°C (59 to 86°F) (see USP Controlled Room Temperature). The solution should be used within 120 minutes of the end of synthesis calibration time.

5.9.3 Dispensing of Study Drug

The dosage administered will be recorded on the CRF.

5.9.4 Return or Destruction of Study Drug

After injection of the C 11 choline the syringe will be assayed for residual radioactivity, to be used in calculation of the precise injected dose. The syringe will then disposed of in the radioactive container for 3-4 hours, about ten half-life durations of C11-Choline (C11-Choline half-life of 20 minutes).

6 Study Procedures

Patients who have completed or will complete diagnostic body CT scan and nuclear medicine bone scan as part of standard care will be recruited and consented for participation in the study

PET/MRI is preferably scheduled 6 weeks after prostate biopsy to minimize the effects of post biopsy hemorrhage.

6.1 Day 0

Informed consent discussion with subject by research coordinator. Consent form signed by subject. Medical records will be reviewed by study coordinator. Subject's eGFR will be determined. If current serum creatinine level is unavailable, labs will be obtained for review.

Subject will be reminded to drink 48 ounces of water the day prior to study procedures. On the morning of the procedure, subjects will be counseled to fast for four hours prior to the procedure and drink 24 ounces of water.

6.2 Day 1

The patient will be screened for MR safety prior to entering the scan room, which may include the use of ferromagnetic screening.

[figure not shown]
1. Vital signs (sitting blood pressure, heart rate, respiratory rate, temperature) are measured by the radiology nurse, who records the results on the source document.
2. Investigator MD or research coordinator to see patient, review vital signs and discuss study objectives, explain the imaging procedures, answer questions. MD will sign and date the source document.
3. Subject is brought to the PET/MR imaging suite. Total dose of 12-14 mCi C-11 choline is injected I.V.
4. Torso PET/MR fusion scan is completed. Imaging time 20-30 minutes.
5. Pelvic mpMRI with PET data of pelvis completed. Imaging time 40-45.
6. Following completion of imaging, subject will return to the relax room and vital signs (sitting blood pressure, heart rate, respiratory rate and temperature) will be re-checked by

the radiology nurse, with the study coordinator recording the data in the source documents.

7. Subject will be discharged.

